	6.5.1 Data and Safety Monitoring Plan.....	35
7	Adverse Event Reporting.....	36
7.1	Definitions.....	36
7.2	Guidelines for Adverse Event Reporting.....	36
8	Other Considerations.....	37
8.1	Clinical Site Eligibility.....	37
8.2	Clinical Site Audits.....	37
8.3	Performance Monitoring.....	37
8.4	Inclusion of Women and Minorities.....	37
8.5	Remote Visits to Enhance Retention.....	37
9	References.....	39
10	Appendix.....	47

Design Synopsis

Primary Objectives

1. To describe surgical risks and changes in clinical, metabolic, and psychosocial measures among patients undergoing bariatric surgery. Risks and changes occurring within 3 years of surgery will be assessed using standardized techniques and measures in a multi-center cohort of patients.
2. To determine the associations of clinical and demographic patient characteristics, components of the surgical procedure, and peri-operative and post-operative care with post-operative risks and changes in clinical, metabolic, and psychosocial measures.

Secondary Objectives

1. To assess health care utilization of patients undergoing bariatric surgery for treatment of obesity and related co-morbidities.
2. To obtain and store biospecimens (serum, plasma, whole blood) for research related to the aims of this study, and for future research into the pathophysiology and genetics of obesity and obesity related complications.

Type of Study

- Prospective cohort

Inclusion Criteria

- Patients who are at least 18 years of age and undergo bariatric surgery by a LABS certified surgeon
- Selected by algorithm to be included in LABS-2

Exclusion Criteria

- Informed consent not obtained
- Prior bariatric surgery
- Unlikely to comply with follow-up protocol
- Unable to communicate with local study staff

Sample Size

- Approximately 2,400 patients recruited over a 3 year period

Duration of Follow-up

- Up to 7 years following bariatric surgery

Outcomes

- Death
- Complications
- Changes in clinical, metabolic, and psychosocial measures

Data Collection Schedule

- The LABS-2 baseline data will be collected within 30 days prior to bariatric surgery.
- Follow-up assessments will occur approximately 30 days, 6 months and 12 months following date of bariatric surgery and annually thereafter.

1 Introduction

1.1 Background. Obesity has become one of the leading health concerns in the United States (US) (Mokdad 2004). The traditional approach to weight loss consisting of diet, exercise, and medication generally achieves no more than a 5-10% reduction in body weight (Yanovski 2002, McTigue 2003) and regain to or above baseline after such weight loss occurs in more than 90% of people undergoing non-operative therapy within five years (Safer 1991, Wadden 1989).

Bariatric surgical procedures, which restrict stomach size or lead to decreased absorption of nutrients, are being increasingly performed to treat extreme obesity. These procedures often result in substantial weight loss and can have a dramatic effect on co-morbidities associated with obesity, such as improved control of blood sugar or even reversal of type 2 diabetes. However, bariatric surgical procedures also carry substantial risks, including death.

Extreme or Class 3 obesity (BMI >40) has dramatically increased in prevalence over the past several decades, now affecting almost 5 percent of the US adult population. Although an increasing number of people with extreme obesity and obesity-related complications are undergoing bariatric surgical procedures, there has been little systematic research to help determine the risks and benefits of bariatric surgery, or to provide guidance on appropriate patient selection. Of the several different types of bariatric procedures performed in the US, the Roux-en-Y gastric bypass (RYGB) (Howard 1995, MacLean 1995, MacLean 1993, Sugerman 1987, Laws 1981, Lechner 1981, Naslund 1986, Naslund 1987, Naslund 1988a, Naslund 1988b, Pories 1982, Hall 1990) is the most commonly performed. The restrictive adjustable gastric band is increasing in use in the US and is the leading procedure performed outside of the US (Johnson 2004). The biliopancreatic diversion (BPD) with or without the duodenal switch (BPD DS) has also grown in use but is performed by a smaller number of practitioners. Growth in the use of any type of bariatric procedure over the last decade has been truly remarkable with over 120,000 procedures performed in 2003 compared to less than 20,000 performed in 1993 (Johnson 2004, Pope 2002). This growth may be related to the reported efficacy of these procedures, the availability of less-invasive laparoscopic procedures, a 10-12% yearly increase in the pool of surgical candidates (as defined by the 1991 National Institutes of Health (NIH) consensus conference criteria), by increased media exposure of celebrity patients who had successful bariatric procedures (Johnson 2004), and the identification of morbid obesity as a life-threatening disease (Calle, 1999; Flegal, 2005).

One of the more challenging issues facing health care providers and patients considering bariatric surgery is a lack of comprehensive and reliable data concerning risk stratification, effectiveness, and global outcomes. To facilitate and accelerate research in this area, the National Institute of Diabetes and Digestive and Kidney Diseases (NIDDK), with the support of the NIH Office of Research On Women's Health, established a Bariatric Surgery Clinical Research Consortium, now known as the Longitudinal Assessment of Bariatric Surgery consortium (LABS). LABS is comprised of six clinical centers and a Data Coordinating Center (DCC) working in cooperation with NIDDK scientific staff to plan, develop,

and conduct coordinated clinical, epidemiological, and behavioral research in the field of bariatric surgery.

Investigative centers in LABS include the University of Pittsburgh Medical Center (Pennsylvania), Columbia-Presbyterian Hospital and Cornell University (New York), East Carolina Medical Center (North Carolina), Neuropsychiatric Research Institute (North Dakota), Oregon Health & Science University and Legacy Good Samaritan Hospital (Oregon), and the University of Washington / Virginia Mason (Washington). The Data Coordinating Center is at the University of Pittsburgh, Graduate School of Public Health.

The overarching goal of LABS is to bring together researchers with expertise in bariatric surgery, obesity research, internal medicine, endocrinology, behavioral science, outcomes research, epidemiology, and other relevant fields to plan and conduct studies that will ultimately lead to a better understanding of bariatric surgery and its impact on the health and well-being of patients with obesity and obesity-related diseases. To achieve this goal, LABS will create and implement standardized measures and data collection instruments for patients undergoing bariatric surgery at participating clinical centers. Rigorously collected information on patient characteristics, surgical procedures, clinical and psychosocial outcomes, and health care utilization will ultimately lead to developing rational recommendations for clinical care. LABS is intended to develop evidence-based information regarding the risks and benefits of bariatric surgery. LABS will also submit serum and plasma specimens to the NIDDK-supported biospecimens repository. These specimens will be used to address the research aims of this study, and to be stored for future research into the pathophysiology of obesity and its complications.

LABS has designed a prospective, longitudinal cohort study with three components. LABS-1 includes all patients who are at least 18 years of age and who undergo bariatric surgery by LABS certified surgeons prior to December 31, 2007, with the primary goal of evaluating the short-term **safety** of bariatric surgery. Important adverse outcomes (i.e., death, rehospitalization, reintervention) occurring within 30 days of surgery are recorded to assess the relationship between short-term morbidity and mortality rates and various patient, operative, and post-surgical care characteristics. LABS-2, described in this protocol, will include a subset of patients from the LABS-1 cohort, with the primary goal of evaluating the longer-term **efficacy** of bariatric surgery. More extensive data collection (i.e. demographic, anthropometric, surgical, clinical, and behavioral) and longer follow-up will allow LABS-2 to identify longer-term safety and efficacy (up to 7 years) outcomes, both risks and benefits, and to determine their associations with patient, surgical, and post-surgical care characteristics. Finally, LABS-3, which will be developed in a series of future protocols, will include selected subsets of patients from the LABS-2 cohort to conduct detailed studies of **mechanisms** involved in weight loss and weight gain, energy expenditure, glucose control, and other aspects of the pathophysiology of obesity and obesity-related complications.

This protocol refers specifically to the LABS-2 component (**efficacy**) of LABS. A detailed description of the LABS-1 and LABS-3 components are addressed in separate protocols.

2 Objectives and hypotheses

2.1 Primary Objective

The primary objective of LABS-2 is to use standardized techniques and measures to assess the longer-term safety and efficacy of bariatric surgery by:

1. comparing post-surgical outcomes to pre-operative status
2. examining risks and benefits of surgery.

LABS-2 will determine the associations between clinical/demographic patient characteristics, components of the surgical procedure, and peri-operative and post-operative care with post-operative risks and changes in patient status.

The principal domains of research interest are delineated below and relate to achieving weight loss and changes in clinical and metabolic co-morbidities of obesity, psychosocial parameters, and quality of life. Additionally, post-operative sequelae as a result of undergoing surgery will be examined. These outcomes will be assessed prospectively for up to 7 years across a multi-center cohort of participants.

Weight Loss and Body Composition. The primary intent of bariatric surgery is to induce weight loss. The ability of bariatric surgery to meet this goal will be assessed by maximum weight loss and long-term patterns of weight loss or regain. LABS-2 will examine differences in weight loss, fat mass and fat-free mass, and waist and neck circumferences based on gender (hypothesizing greater weight loss in men (Ballantyne 2003)), diabetes mellitus (hypothesizing less weight loss among patients with diabetes (Perugini 2003, Schauer 2003)), pre-operative and post-operative physical activity level (hypothesizing a direct relationship between activity and weight loss (Boan 2004)), and surgical technique (hypothesizing greater weight loss maintenance with longer length of the bypass limb in gastric bypass surgery (Choban 2002, Brolin 2002)).

Diabetes Mellitus and Insulin Resistance. Type 2 diabetes mellitus (T2DM), the metabolic syndrome, and insulin resistance (IR) are common metabolic co-morbidities of obesity (Curtis 2005). Assessing the longer-term efficacy of bariatric surgery with respect to T2DM will be based on a clinical history of medication use and on serial measurements of HbA1c. Assessing efficacy for metabolic syndrome and IR will be based on changes in fasting glucose, insulin, lipoprotein profiles, resting blood pressure, waist circumference and clinical history of medications for treatment of hyperglycemia, hypertension, and dyslipidemia.

It is hypothesized that improvement of T2DM, metabolic syndrome, and IR will be related to maximal weight loss, maximal loss of fat mass, nadir BMI and physical activity level (Sjostrom 1999, Cummings 2004, Sugerma 2003, Greenway 2002, Orchard 2005).

Cardiovascular and Pulmonary Disease. Obesity is a risk factor for cardiovascular diseases (CVD) and sleep apnea (Guisti 2004, de Leiva 1998, Koch 1999, Valencia-Flores 2004, Vendrell 2004, Infanger 2003, Buchwald 2004). To assess the efficacy of bariatric surgery with respect to CVD, changes in the traditional factors listed above for IR as well as high-sensitivity C - reactive protein (hsCRP), a marker of systemic inflammation, will be measured. It is hypothesized that improvement of

CVD factors will be related to maximal weight loss, maximal loss of fat mass, and nadir BMI post surgery (Christ 2004, Reinehr 2004, Blumenthal 2000, Stefanick 1998, Schotte 1990). In addition, change in cardiac function will be measured by the time to complete a 400 meter corridor walk. It is hypothesized that the time to complete the 400 meter corridor walk will be directly related to age, degree of obesity (body mass index [BMI]), sex (longer in females), physical activity level, measures of diabetes mellitus (DM) and insulin resistance (IR), blood pressure (BP), liver function tests, inflammatory markers, and sleep apnea (Newman 2003). Furthermore, the time to complete the corridor walk is hypothesized to predict future events such that increased time or inability to complete the walk is related to subsequent cardiovascular clinical events and mortality (Miyamoto 2000, Zugck 2000). We will also evaluate the incidence of coronary heart disease, defined as sudden death, myocardial infarction or need for coronary revascularization post surgery. It is hypothesized that patients who are male and patients who have unchanging metabolic profiles associated with diabetes or PCOS will be at higher risk (Talbot 2004, Kannel 1979).

The prevalence of sleep apnea and changes from baseline status will be assessed by self-report via the Berlin Sleep Questionnaire and by use of continuous or bilevel positive airway pressure machines (CPAP or BiPAP). It is hypothesized that weight loss and reductions in neck circumference will be associated with improvements in sleep apnea.

Renal Disease. Obesity causes and complicates diabetes and hypertension, the two most common causes of kidney failure (Wiggins 2005). Furthermore, obesity in its own right can cause renal disease and may accelerate injury in glomerulonephritides (De Jong 2002). The mechanisms for the adverse effects of obesity on the kidney include its hypertensive and diabetogenic effects. Additionally, adipogenic hormones may have direct injurious actions in the kidney (Coresh 2004). Thus, weight loss is likely to improve indices of renal function. However, bariatric surgery itself has been associated with progressive renal disease through a variety of mechanisms (Khurana 2004). Renal function will be measured by serum creatinine and cystatin and urinary albumin and creatinine (spot urine).

It is hypothesized that albuminuria, the most sensitive index of chronic kidney disease, will diminish after successful bariatric surgery and that the renal function as reflected by serum creatinine will remain stable after successful bariatric surgery (Holzwarth 2002).

Liver Function and Size. The apparent increased prevalence of various forms of non-alcoholic fatty liver disease (NAFLD) in the obese population (Haynes 2004), and the growing identification of NAFLD when sought by liver biopsy among patients undergoing bariatric surgical procedures (Abrams, 2004) have both been the subject of recent publications. The limited data available thus far indicate that it would be important to determine the presence of NAFLD and define the prevalence of advanced forms, such as non-alcoholic steatohepatitis (NASH) and cryptogenic cirrhosis, by systematic intra-operative liver biopsy in a well defined bariatric surgical population. When a liver biopsy is taken during surgery as part of the clinical institution's standard practice, a portion will be studied by LABS investigators. The thickness of the left lobe of the liver will be assessed using a standardized measuring technique.

It is hypothesized that the prevalence and severity of the spectrum of non-alcoholic fatty liver disease are underestimated by traditional laboratory parameters, clinical assessment, and intra-operative visual inspection of the liver (Gholam 2002, Spaulding 2003). Additionally, it is hypothesized that severity of

the liver disease detected on intra-operative biopsy will correlate with short-term post-operative morbidity and mortality and that significant steatohepatitis detected on intra-operative biopsy will correlate with clinical and biochemical worsening of liver disease during periods of rapid post-operative weight loss (Capron 1982, Bradbury 2004). It is also hypothesized that hepatic iron accumulation in the fatty liver disease of the bariatric surgery population will be associated with more severe fibrosis (George, 1998). Furthermore, it is hypothesized that the prevalence and severity of fatty liver disease, controlled for age, BMI, and diabetes, will vary across racial and ethnic groups with the prediction that the most severe findings will occur in patients of Hispanic ethnicity, followed by non-Hispanic Caucasians, followed by African Americans, and that a multivariable combination of traditional clinical, demographic and laboratory assessments can be helpful in predicting the severity of NAFLD in obese patients (Ruhl, 2004).

We also hypothesize that increased liver size at the time of operation is associated with a higher rate of failed laparoscopic procedures due to problematic visualization of the gastroesophageal junction, a higher rate of intraoperative bleeding complications and that presurgical weight loss is associated with decreased liver size. To test these hypotheses we will assess the relationship of liver thickness, the rate of failed laparoscopic procedures secondary to visualization, the rate of liver bleeding and repair and pre-operative weight loss.

Behavioral Factors. Evidence suggests that pre-existing psychological and behavioral problems influence the outcomes, both short-term and long-term, of bariatric surgery (Herpertz 2004). In particular, it is hypothesized that subjects who have active untreated problems with alcohol or drug abuse, problems with binge eating, or problems with untreated depression will experience higher rates of surgical post-operative medical complications, less weight loss (Hsu 1998, Hsu 1996, Hsu 1997, Green 2004, Averbukh 2003), and less relative improvement in social functioning, quality of life, depression, and overall psychological status (Green 2004), while those who intentionally lose weight pre-operatively (van de Weijert 1999) and those with more family/social support (Ray 2003, Hildebrandt 1998) will achieve greater weight loss. Furthermore, it is hypothesized that bariatric surgery will result in substantial improvements in social functioning (Choban 1999), quality of life (Dymek 2001), depression (Dixon 2003, Dymek 2001), and overall psychological status (Hsu 1998). The magnitude of the improvement in these parameters will positively correlate with the degree of weight loss. Additionally, depression that reoccurs or develops post-operatively will be associated with decreased improvement in quality of life (Moore 2005).

Gender Issues. Potential gender differences in longer-term efficacy of bariatric surgery for weight loss, maintenance of weight loss, prevalence of T2DM, parameters of metabolic syndrome, insulin resistance and magnitude of CVD risk factors will be examined. It is hypothesized that baseline insulin resistance severity will be more important than gender as a predictor of efficacy of bariatric surgery for DM and CVD risk factors. LABS-2 will also examine whether changes in sexual functioning are related to weight loss (Larsen 1990, Camps 1996, Trischitta 2003)

Women's Health. Women constitute the majority of patients who undergo bariatric surgery. Obesity is a risk factor for several health conditions specific to, or more common among, women, such as menstrual abnormalities (Norman 2004), infertility (Norman 2004), and urinary incontinence (Kapoor 2004). It is hypothesized that menstrual abnormalities (Crosignani 2003), fertility (Gerrits 2003), symptoms of polycystic ovarian diseases (Crosignani 2003), and urinary incontinence (Sugerman 2001)

will resolve following bariatric surgery. However, menstrual abnormalities may increase or show no improvement in the first 12 months following surgery when weight loss is often rapid (Schuetz 2004).

Risks of Bariatric Surgery. Bariatric surgeries impart potential long-term risks that are not necessarily faced by those who do not undergo such procedures or that differ depending on aspects of the surgical procedure (Deveney 2004). Thus, potential adverse outcomes such as death, outlet obstruction, wound complications, and surgical revisions and re-operations will be tracked. Pre-operative characteristics including demographics (e.g., sex, race), BMI, and co-morbidities will be examined for their relationships with these outcomes (Perugini 2003, Liu 2003, Livingston 2002). Additionally, the occurrence of stomal ulcer, PE/DVT, and dehydration will be examined in relationship to limb length, pouch size, and types of anastomoses used in the gastric bypass procedure. Hypotheses related to surgical risk are that males will have higher mortality than females, wound infections are more common among patients who undergo an open or laparoscopic converted to open bariatric surgery than among patients undergoing a laparoscopic procedure, that nutritional complications, including re-admission to hospital, will be more common in patients undergoing more malabsorptive operations than among those undergoing a more restrictive operation, that total morbidity is higher in males than females and is positively associated with pre-operative BMI, that African-Americans will have lower percent excess weight loss results following bariatric surgery than patients in other racial groups, and that patients who undergo bariatric surgery without any pre-operative thromboembolism prophylaxis will experience a higher deep vein thrombosis or pulmonary embolism rate than patients who do receive pre-operative prophylaxis.

Nutrient Deficiencies. Another potential long-term risk of bariatric surgery is nutrient deficiency (Alvarez-Leite 2004). LABS-2 will investigate micro-nutrient and macro-nutrient deficiencies by surgical procedure, hypothesizing more frequent occurrences with malabsorptive procedures (Brolin 2002, Ortega 2004, Skroubis 2002, Coates 2004, Faintuch 2004) and by various components of surgery (e.g., limb length, pouch size, and type of anastomoses in bypass surgeries (Brolin 2002, Chobin 2002)). Specifically, protein malnutrition secondary to deficient intake or malabsorption is hypothesized to occur from rapid weight loss, clinically important anemias are hypothesized to be due to a deficiency of vitamin B12 or iron, fat soluble vitamin deficiencies are hypothesized to be more frequent in patients undergoing duodenal switch procedures, and deficiencies of micronutrients related to bone health are hypothesized to be more frequent among patients with malabsorptive operative procedures.

Work Productivity and Activity. Obese workers have the highest prevalence of work limitations (6.9% vs. 3.0% among normal-weight workers) (Hertz 2004) and weight reduction interventions appear to increase productivity (Sartorio 2003). Severe obesity increases the number of work loss days and is an important factor in the workplace (Pronk 2004, Bungum 2003). The effects of weight loss surgery on productivity at work, absenteeism and presenteeism have not been well studied. It is hypothesized that patients undergoing bariatric surgery will have fewer days lost to work secondary to obesity compared with presurgery, that productivity at work, as measured by absenteeism and presenteeism, will be improved after surgery, and that the size of these effects will be associated with the extent of weight loss and the degree of initial obesity.

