Variable	Measurement	Variable(s)	Measurement		
Weight Loss and Body Composition:					
Max. weight loss	Continuous	Gender, diabetes, surgical technique	Categorical	Patient	Analysis of covariance (ANCOVA)
Max. Δ in fat mass	Continuous				
Max. Δ in fat free mass	Continuous	Physical activity level (pre-op and post-op)	Continuous	Patient	Linear regression
Max. Δ in waist circumference	Continuous				
Max. Δ in neck circumference	Continuous				
Patterns of weight loss	Continuous	SAME AS ABOVE	SAME AS ABOVE	Visit	Linear mixed models, piece-wise linear mixed models, non-linear hierarchical models
Pattern of weight regain	Continuous				
Diabetes Mellitus & Insulin Resistance:					
Reduction in diabetes	Categorical	Maximal weight loss, maximal loss of fat mass, nadir BMI	Continuous	Patient/Visit	Logistic regression, Discrete-time proportional hazards (pooled logistic regression)
Reduction in met. syndrome	Categorical				
Δ in insulin resistance	Continuous				
CVD and Pulmonary Disease:					
Corridor walk time	Continuous	Age, BMI, insulin resistance, blood pressure, liver function, inflammatory markers	Continuous	Patient	Spearman correlation, linear regression
Corridor walk time	Continuous	Gender, diabetes, sleep apnea	Categorical	Patient	ANCOVA
Incident CVD, mortality	Categorical				
Renal Disease:					
Δ in albuminuria	Continuous	Pre/post bariatric surgery	Continuous	Patient	Paired t-tests or analogous non-parametric methods
Δ in GFR	Continuous	Pre/post bariatric surgery	Continuous	Patient	

Table 4.1. (continued). Primary Analytic Methods Used to Evaluate LABS-2 Hypotheses

Outcome Variable	Measurement	Predictor Variable(s)	Measurement	Unit of Analysis	Primary Method(s) Of Analysis
Liver Function:					
Prevalence/severity of non-alcoholic fatty liver disease (NAFLD) (based on histology)	Categorical	Traditional assessment of NAFLD (labs, clinical assessment, visual inspection)	Categorical	Patient	Kappa statistic, predictive value negative
		Race/ethnicity, traditional demographic, clinical, and laboratory assessments	Categorical and continuous	Patient	Binomial and ordinal logistic regression
Short-term post-operative morbidity and mortality	Categorical	Severity of liver disease (biopsy)	Categorical	Patient	Poisson regression
Δ in liver disease (clinical and biochemical)	Continuous	Steatohepatitis (detected on biopsy), weight loss	Categorical	Patient/visit	Linear regression / linear mixed models

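### Waist circumference is part of the metabolic syndrome outcome that is tested against weight loss, so that test can be positive through waist alone

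*Protocol*

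**What the plan says.** In Section 2.1, the paragraph on diabetes and insulin resistance (IR) sets out what the assessment uses: "Assessing efficacy for metabolic syndrome and IR will be based on changes in fasting glucose, insulin, lipoprotein profiles, resting blood pressure, waist circumference", plus history of medication for glucose, blood pressure and lipids. Type 2 diabetes is assessed separately, by medication use and HbA1c.

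The hypothesis follows: "improvement of T2DM, metabolic syndrome, and IR will be related to maximal weight loss, maximal loss of fat mass, nadir BMI", with physical activity level as a further predictor.

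Table 4.1 turns this into a planned analysis. Under diabetes and insulin resistance, the outcome "Reduction in met. syndrome" is categorical and the predictors are "Maximal weight loss, maximal loss of fat mass, nadir BMI". The methods are logistic regression and discrete-time proportional hazards (pooled logistic regression). Change in insulin resistance is a separate, continuous outcome in the same block.

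The same table lists "Max. Δ in waist circumference" under weight loss and body composition, in the block that contains maximal weight loss and change in fat mass. Nothing in the protocol removes waist from the metabolic syndrome outcome or plans a version without it.

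**The concern.** The question of interest is whether the metabolic complications of obesity improve more in patients who lose more weight. One component of the syndrome, waist, is itself a measure of adiposity, and the protocol classes it as body composition elsewhere. Patients who lose more weight are more likely to drop below a waist cut-off. Some of them then stop meeting the definition although their glucose, lipids and blood pressure have not changed.

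A significant odds ratio from the planned model therefore has two explanations: metabolic improvement that rises with weight loss, or a smaller waist in those who lost more weight. The planned test cannot tell them apart. A large cohort does not help, because it makes the overlap easier to detect.

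**Working it through.** The protocol gives no figure for this point, so there is none to reproduce. The check is in three steps.

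**1. Mechanism.** Assume the syndrome means at least 3 of 5 components, one being waist. A patient with waist plus exactly two others scores 1 + 2 = 3 before surgery. If only waist falls below its cut-off, the score becomes 0 + 2 = 2 and the syndrome counts as resolved. Patients with waist plus three or four others score at least 3 without waist, so waist alone does not reclassify them. The size of the effect depends on how many patients cross the waist cut-off while at the count threshold.

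**2. Simulation with non-waist components that do not respond to surgery or weight loss.**

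- From the protocol: target of 2,400 (Section 4.4.1); 84% women (Section 3.2.6); two-sided alpha 0.05 (Section 4.2). The smaller size is 2,400 × (1 − 0.25) = 1,800, the upper loss to follow-up in Section 4.4.1.
- Assumed: 3-of-5 rule; cut-offs 88 cm (women) and 102 cm (men); mean baseline waist 115 to 135 cm in women, 15 cm more in men, SD 14; weight loss L with mean 28% and SD 10; each of the four other components present in 50% and changing state at random with probability 0.10.
- Waist reduction (%) = 0.75 × 28 + 8 × [r z + √(1 − r²) e] = 21 + 8 × [r z + √(1 − r²) e]. Here z = (L − 28)/10, e is independent standard normal noise and r is the correlation of waist loss with weight loss.
- Model, in patients with the syndrome at baseline: logit P(resolved) = a + b z. The OR per SD of weight loss is exp(b). There were 300 runs per setting.

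Results at 2,400 (median OR; share of runs with p < 0.05):

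| Mean waist, women | Cross cut-off | r = 0.3 | r = 0.6 | r = 0.8 |
|---|---|---|---|---|
| 115 cm | 43% | 1.18; 76% | 1.39; 100% | 1.56; 100% |
| 125 cm | 25% | 1.19; 72% | 1.43; 100% | 1.61; 100% |
| 135 cm | 12% | 1.17; 48% | 1.36; 96% | 1.49; >99% |

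At 1,800 the OR is 1.16 to 1.60 and rejection 36% to 100%. Further settings at 2,400:

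- Component prevalence 35% or 65% (125 cm, r = 0.6): OR 1.42 and 1.40, rejection 100%.
- Mean waist 150 cm, 3% crossing (r = 0.6): OR 1.15, rejection 34%.
- r = 0: OR 1.00, rejection 5%, so the association disappears.
- Waist removed (outcome: 2 or more of the four other components): OR 0.98 to 1.02 and rejection 3% to 7% over both sample sizes in the main grid, and 1% to 6% in the further settings. At a true 5%, the simulation error is √(0.05 × 0.95/300) = 1.3 points.

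**3. Simulation with components that do resolve, but independently of the amount of weight lost.** Assumed: 1,300 patients with the syndrome at baseline; the other components at 60% to 70% prevalence, 60% persisting and 8% new onset; waist 120 to 135 cm, falling about 0.8 cm per 1% of weight lost; the same rule and cut-offs; 200 to 300 runs.

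| Still above waist cut-off | Rejection with waist |
|---|---|
| 67–85% | 75–100% (OR 1.18–1.29 per SD) |
| 90% | 53% |
| 96% | 15% |

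Using only the non-waist components, rejection is 4% to 7%.

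**The case against.** The best reply is that waist belongs to the conventional definition and that the hypothesis names the syndrome itself. A fall in waist is then a legitimate part of improvement. Type 2 diabetes is tested against the same predictors without waist, and Section 2.1 names glucose, insulin, lipids and blood pressure individually, so component results could be reported. Section 4.1 leaves the final approach for each hypothesis open, an operational definition is commonly left to the analysis plan, and every magnitude above is assumed.

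Much of this stands. The sizes are illustrative, and the conventional outcome should not be dropped. It does not remove the point: the protocol itself fixes waist among the assessed items, fixes the predictors and names the method. The diabetes outcome says nothing about lipids or blood pressure.

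A reader might infer three stronger claims that the protocol does not support:

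- **CVD factors.** Section 2.1 measures "changes in the traditional factors listed above for IR as well as high-sensitivity C - reactive protein (hsCRP") and expects that "CVD factors will be related to maximal weight loss, maximal loss of fat mass, and nadir BMI post surgery". Waist is carried over, but no composite is defined, and glucose, lipids, blood pressure and hsCRP analysed separately contain no waist. Table 4.1 has no row testing CVD factors against weight loss. Its row for change in CVD risk factors is under gender issues, with gender and insulin resistance severity as predictors. Only the waist item itself overlaps.
- **Insulin resistance.** The list in Section 2.1 is shared with metabolic syndrome and does not say that waist enters an IR measure. The outcome is affected only if it does.
- **A spurious association is bound to appear.** It is not: rejection was 15% and 34% where few patients crossed the cut-off, and nominal when waist loss was unrelated to weight loss.

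**Conclusion.** The point holds for metabolic syndrome and only there. With waist in the outcome, the planned regression on weight loss, fat loss or nadir BMI can reject even when improvement in glucose, lipids and blood pressure is unrelated to the amount of weight lost. Wherever waist loss was tied to weight loss, the rejection rate lay between about 15% and 100%; removing waist brought it back to roughly 5%. The range rests on an assumed 3-of-5 rule, assumed cut-offs, baseline waist and component rates, and a linear link simulated for weight loss only. Fat loss and nadir BMI are covered by the same reasoning, not by a separate calculation.

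A positive result remains valid evidence about the syndrome as conventionally defined. On its own it does not show that greater weight loss brings greater metabolic benefit. The type 2 diabetes outcome is unaffected.

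**What to change.** In the hypothesis paragraph of Section 2.1 (Diabetes Mellitus and Insulin Resistance) and in the metabolic syndrome row of Table 4.1:

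- Keep the conventional definition for describing prevalence and resolution, and as an analysed outcome.
- Where the predictor is maximal weight loss, maximal fat loss or nadir BMI, also analyse the non-waist components (glucose, lipids and blood pressure, with their medications), for example as the change in their count.
- State that any conclusion about the metabolic benefit of greater weight loss rests on the waist-free result.

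The cost is one derived variable from data already collected and one further analysis. The waist-free result is not the conventional syndrome and so compares less directly with studies that use that definition, which is why both should be reported.
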